## 6.3 Follow-up telephone contact

Clinical research staff will make follow-up telephone calls to study participants on days 30  $\pm$  7, 60  $\pm$  7, and 90  $\pm$  7 after completion of Study Visit 6 (or earlier if study agent discontinued prior to completion) to assess symptoms and adverse events.

		Month 0	Month 1	Month 3	Month 6	Month 9	Month 12	30, 60, 90 days	Unscheduled Liver
Study Activity/Measurement	Screen 1	Study Visit 1	Study Visit 2	Study Visit 3	Study Visit 4	Study Visit 5	Study Visit 6	Follow-up Calls ^	Liver Transplant %
Review subject eligibility criteria	Х								
Obtain informed consent and HIPPA authorization	Х								
Pregnancy test	Х								
Imaging review	Х		Х	Х	Х	Х	Х		
Registration/randomization	Х								
Medical history		Х	Х	Х	Х	Х	Х		
Concomitant medication review		X	Х	Х	Х	Х	Х		
Physical assessment	Х				Х		Х		
Health assessment		Х	Х	Х		Х			
Baseline symptom assessment		Х							
Blood chemistry	Х	Х	Х		Х		Х		
Prothrombin time	Х						Х		
Creatine kinase		Х							
Hemoglobin A1c (glycated hemoglobin)		Х			Х		Х		
Lipid panel		Х	Х				Х		
Serum AFP test	Х				Х		Х		
Liver stiffness		Х					Х		
Liver fat fraction		Х					Х		
Research blood specimen		Х			Х		Х		Х
Baseline risk factor questionnaire		X							
Follow-up risk factor questionnaire					Х		Х		
Dispense study drug and diary with instructions		Х	Х	Х	Х	Х			
Symptom/adverse event assessment			Х	Х	Х	Х	Х	Х	
Collection and review agent and diary, assess medication compliance			Х	Х	Х	Х	Х		
Telephone contact #	Х			Once a	a Month			Х	Х
Transplant tissue specimen									Х

## 6.4 Schedule of Events Table

+ Abdominal imaging results will be reviewed during pre-screen medical chart review to determine initial eligibility. At study visits 3-6, all standard of care images occurring since screening or the last study visit will be reviewed.

#Telephone contact once a month ( $\pm$  3 days) during the intervention to assess compliance and adverse events.

^Follow-up telephone contact on days  $30 \pm 7$ ,  $60 \pm 7$ , and  $90 \pm 7$  after completion of Study Visit 6 to assess adverse events.

% Unscheduled liver transplant may occur at any time post-intervention depending on the date of the transplant.

## 6.5 Clinical Laboratory Minimum Test Requirements

Blood Chemistry	Lipid Panel	Other Blood Tests
Alanine aminotransferase	Total cholesterol	Hemoglobin A1C (HbA1C)
(ALT (SGPT))	High density lipoprotein (HDL)	Creatine phosphokinase
Aspartate aminotransferase	cholesterol	(CPK)
(AST (SGOT))	Low density lipoprotein (LDL)	Prothrombin Time (PT/INR)
Alkaline phosphatase (ALP)	cholesterol	Alpha-fetoprotein (AFP)
Bilirubin, total	Triglycerides	
Creatinine		
Glucose		
Sodium		

## 6.6 Off Agent Criteria

Participants may stop taking study agent for the following reasons:

- Completed the protocol-prescribed intervention
- Adverse event or serious adverse event
- Inadequate agent supply
- Noncompliance/refusal due to non-medical reasons
- Concomitant medications
- Medical contraindication
- Receive a liver transplant prior to completion of the intervention

Participants will continue to be followed, if possible, for safety reasons and in order to collect endpoint data according to the schedule of events. As described in section 6.3, clinical research staff will follow participants by telephone on days  $30 \pm 7$ ,  $60 \pm 7$ , and  $90 \pm 7$  after the participant discontinues the study agent to assess symptoms and adverse events. Standard of care data (medical history, laboratory test results, concomitant medications, HCC surveillance data) will continue to be collected via review of the participant's electronic medical record at the time points specified in the Schedule of Time and Events.

## 6.7 Removal of Subjects from Study

Patients can be taken off the study treatment and/or study at any time at their own request, or they may be withdrawn at the discretion of the investigator for safety, behavioral or administrative reasons. The reason(s) for discontinuation will be documented and may include:

- Patient voluntarily withdraws (follow-up permitted);
- Patient withdraws consent (termination of treatment and follow-up);
- Patient is unable to comply with protocol requirements;
- Patient demonstrates recurrence of HCC (unless continued treatment with study drug is deemed appropriate at the discretion of the investigator);
- Patient experiences toxicity that makes continuation in the protocol unsafe;

- Treating physician judges continuation on the study would not be in the patient's best interest;
- Patient becomes pregnant (pregnancy to be reported along same timelines as a serious adverse event);
- Development of second primary malignancy (basal/squamous cell skin cancer, or prostate cancer with a Gleason score 6 or less) that requires treatment, which would interfere with this study;
- Lost to follow-up. If a research subject cannot be located to document survival after a period of 2 years, the subject may be considered "lost to follow-up." All attempts to contact the subject during the two years must be documented and approved by the Data Monitoring Committee.

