## 5.10 Removal of Patients from Protocol

Patients will be removed from the study when any of the criteria listed in Section 6.7 apply. Notify the Principal Investigator, and document the reason for study removal and the date the patient was removed in the Case Report Form. The patient should be followed-up per protocol (Section 6.3).

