# 9.3.2 Analysis of Secondary Endpoints RFS and OS

For the secondary objective, comparison of overall survival and recurrence free survival between the pravastatin and placebo groups will be achieved by fitting a Cox proportional hazards model as described above for TTR. In this analysis, a competing risk model will

be fitted to the data using time to transplant only as a competing risk since overall survival includes death from any cause.

**Waitlist drop-off.** Fischer's exact test will be used to compare the proportions of patients on the waitlist who drop off between the pravastatin and placebo group. We expect about 35% of patients in the placebo group to drop off due to various causes such as death and HCC progression beyond Milan. Data from 47 patients per group achieve 80% power to detect a decrease in drop-off rates from 35% in the control group to 14% in the treatment group using a one-sided Fisher's exact test at the 0.1 level of significance.

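### Sections 5.10, 6.3, 6.6 and 6.7 conflict on follow-up after HCC recurrence, so deaths and waitlist drop-offs more than about 90 days after recurrence may go unobserved

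*Combined protocol and SAP*

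**What the plan says.** All references are to the combined protocol and SAP.

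- **Section 6.7** opens permissively: "Patients can be taken off the study treatment and/or study at any time at their own request". Its list of possible reasons includes "Patient demonstrates recurrence of HCC (unless continued treatment with study drug is deemed appropriate at the discretion of the investigator".
- **Section 5.10** is mandatory and refers to the study, not the treatment: "Patients will be removed from the study when any of the criteria listed in Section 6.7 apply". It continues: "The patient should be followed-up per protocol (Section 6.3".
- **Section 6.3** consists of calls at days 30, 60 and 90 after Visit 6, "or earlier if study agent discontinued prior to completion) to assess symptoms and adverse events". It names neither vital status nor waitlist status.
- **Section 6.6** covers patients who stop the agent: "Participants will continue to be followed, if possible, for safety reasons and in order to collect endpoint data according to the schedule of events". It adds chart review at the scheduled time points. Recurrence is not on its list of reasons.
- **Section 2.3** defines overall survival (OS) as time from randomisation to death from any cause. It defines waitlist drop-off as progression outside Milan/T2, becoming too sick to transplant, or death.
- **Section 9.3.2** compares waitlist drop-off as proportions with Fisher's exact test. For OS it fits a competing-risk model "using time to transplant only as a competing risk since overall survival includes death from any cause".

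**The concern.** Recurrence is the primary event, and a large minority of patients is expected to have it within the year. A site following 5.10 would take such a patient off study and make three safety calls. A site following 6.7 could stop treatment only and keep collecting endpoints. Both would be compliant, and no section says that vital or waitlist status is followed to month 12 after a recurrence.

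Two secondary endpoints are exposed. Ending OS follow-up at recurrence is informative censoring if recurrence raises mortality. Waitlist drop-off is compared as proportions, so the problem there is uncounted events, not censoring. If pravastatin delays recurrence, more of this information would be lost on placebo, which pulls the comparison towards no difference.

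A separate inconsistency concerns OS and transplant. A competing event should preclude the event of interest. Transplant does not preclude death, and Section 1.1 itself describes fatal recurrence after transplant.

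**Working it through.** **1. The plan's own figures.** Exact enumeration of the one-sided Fisher test (47 per group, 35% versus 14%, alpha 0.1; Section 9.3.2) gives 81.4% power against the stated 80%, so the figure reproduces. For recurrence, Section 9.3.1 gives 35% in controls and a hazard ratio of 0.45: 1 − exp(0.45 × ln 0.65) = 17.6%, matching the stated 18%.

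**2. Who would lose follow-up.** The inputs from Section 9.3.1 are 12-month control recurrence of 35%, hazard ratio 0.45 and 12-month death of 10%; 65 per arm comes from Section 9.2. Assumptions: exponential times; every recurrence leads to removal; the calls cover 3 months after recurrence; transplant is ignored; mortality after recurrence is m times that before. The documents give no value for m, so 1, 2 and 4 are shown.

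Per year, recurrence λ = −ln 0.65 = 0.431 on placebo and 0.45 × 0.431 = 0.194 on pravastatin; death μ = −ln 0.90 = 0.105.

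The share who recur before month 9 and are alive 3 months later is

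λ/(λ+μ) × [1 − exp(−0.75(λ+μ))] × exp(−0.25mμ).

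At m = 2:
- Placebo: 0.8035 × 0.3311 × 0.9487 = 25.2%, or 16.4 of 65.
- Pravastatin: 0.6479 × 0.2010 × 0.9487 = 12.3%, or 8.0 of 65.

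**3. Deaths unseen, and the effect on the comparison.** Unseen deaths per arm = 65 × ∫ from 0 to 0.75 of λ exp(−(λ+μ)t) exp(−0.25mμ) [1 − exp(−mμ(0.75−t))] dt. The death rate ratio is pravastatin over placebo, deaths divided by person-time, with follow-up either to month 12 or ended 3 months after recurrence.

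| m (assumed) | Lose follow-up, placebo / pravastatin | Unseen deaths of 65, placebo / pravastatin | Share of 12-month deaths unseen, placebo / pravastatin | Death rate ratio, full → cut short |
|---|---|---|---|---|
| 1 | 25.9% / 12.7% | 0.7 / 0.3 | 11% / 5% | 1.00 → 1.00 |
| 2 | 25.2% / 12.3% | 1.3 / 0.6 | 17% / 9% | 0.92 → 0.96 |
| 4 | 23.9% / 11.7% | 2.4 / 1.1 | 25% / 14% | 0.83 → 0.89 |

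**4. Cross-check with competing events.** Take 35% and 20% as cumulative incidences at 12 months (20% is transplant plus death, Section 9.3.1). The total hazard is −ln 0.45 = 0.799, of which recurrence is 0.799 × 35/55 = 0.508 and competing events 0.290. Recurrences by month 12 are 22.8 and 11.6 of 65. Time more than 90 days after recurrence but before month 12 is 92 and 44 patient-months, or 11.8% and 5.7% of 65 × 12 = 780 per arm. This is again about 2 to 1. With 35% and 20% read as marginal rates, the figures are 81 and 38.

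**5. Waitlist drop-off.** If a share q of drop-offs went uncounted, equally in both arms, Fisher power would be 81% at q = 0, 77% at 10%, 68% at 25% and 51% at 50%. The documents give no value for q, so this shows sensitivity and is not an estimate.

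**6. Transplant and OS.** At the plan's 10%, about 0.10 × 65 = 6.5 patients per arm are transplanted by month 12. Their later deaths count under the Section 2.3 definition but not as OS events under the Section 9.3.2 model. The documents give no post-transplant death rate for this window, so the effect is not sized.

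**The case against.** The strongest reply is that the protocol probably intends to keep following these patients.

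- Section 6.7 says treatment and/or study, and presents its reasons as ones that may apply.
- The recurrence item's exception is about continuing study drug, so it can be read as a treatment criterion.
- Only withdrawal of consent is marked as ending follow-up, and loss to follow-up is declared only after two years of failing to document survival.
- Section 6.6 pairs the same 6.3 calls with continued endpoint collection, so citing 6.3 does not by itself switch off chart review.
- Sections 5.9 and 6.2.8 collect specimens from all entrants transplanted before the five-year study ends, which implies tracking beyond recurrence.

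All of this stands, and it makes the loss possible, not established. It does not remove the conflict: 5.10 turns the 6.7 list into a mandatory off-study rule, 6.6 is qualified by feasibility and omits recurrence, and its chart-review items do not name vital or waitlist status. The two-year clause schedules no survival contact, and Section 4.5 declares loss to follow-up after two months of rescheduling.

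The size is also modest. The counts are small, the multipliers are assumed, and at equal mortality the death rate ratio does not move. OS carries no power claim. Some waitlist events occur at recurrence and would be seen, and under Section 4.4 some participants may not be listed.

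A reader might infer that recurrence necessarily ends OS and waitlist follow-up, and does so more often on placebo. The documents support neither as a fact. Removal is one of two available readings, and the imbalance follows only from the design alternative.

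**Conclusion.** The four sections contradict each other on follow-up after recurrence, and post-recurrence ascertainment of OS and waitlist drop-off is not secured. If 5.10 is applied to every recurrence at the design rates, about 16 placebo and 8 pravastatin patients of 65 lose follow-up before month 12. The resulting bias in OS is towards no difference and depends on assumed post-recurrence mortality: none at 1×, 0.92 to 0.96 at 2×, and 0.83 to 0.89 at 4×. With no treatment effect on recurrence the removals balance. Time to recurrence and its power are unaffected, because that endpoint ends at the recurrence.

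This should be corrected, but it concerns secondary endpoints and does not threaten the primary analysis. The handling of transplant in the OS model is a separate mismatch with the OS definition and stands whichever reading of 5.10 is adopted.

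**What to change.** 1. Reconcile 5.10, 6.3, 6.6 and 6.7 so that leaving study treatment and leaving the study are distinct. The treatment decision at recurrence stays as written.
2. State that only withdrawal of consent or true loss to follow-up ends endpoint follow-up, and define loss to follow-up once, since 4.5 and 6.7 differ.
3. Collect vital status and waitlist status to month 12 from the medical record for all randomised patients.
4. In 9.3.2, count deaths after transplant in the main OS analysis and keep the transplant-as-competing-risk model as a sensitivity analysis.

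The cost is protocol wording plus a record check on about 24 patients (16 + 8), using the chart review that 6.6 already describes. With status followed to month 12, the follow-up loss calculated above falls to zero in both arms, apart from withdrawn consent and true loss to follow-up.

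### Sections 5.10, 6.6 and 6.7 conflict on whether endpoint follow-up continues when a patient without recurrence stops for toxicity or non-compliance, so some TTR events may not be captured

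*Combined protocol and SAP*

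**What the plan says.** Three sections cover a patient who stops before any recurrence.

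- **Section 6.6 (Off Agent Criteria)** lists adverse events and "Noncompliance/refusal due to non-medical reasons" among the reasons for stopping the agent. It then says: "Participants will continue to be followed, if possible, for safety reasons and in order to collect endpoint data according to the schedule of events". HCC surveillance data continue to be taken from the medical record.
- **Section 6.7 (Removal of Subjects from Study)** opens with "Patients can be taken off the study treatment and/or study at any time at their own request", or at the investigator's discretion. Its reasons include "Patient experiences toxicity that makes continuation in the protocol unsafe" and "Patient is unable to comply with protocol requirements". Only the two withdrawal reasons say what happens to follow-up.
- **Section 5.10** states: "Patients will be removed from the study when any of the criteria listed in Section 6.7 apply". It refers these patients to Section 6.3, which consists of telephone calls at about 30, 60 and 90 days for symptoms and adverse events.

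Two other places decide how such a patient enters the analysis. Section 2.3 censors TTR at the last evaluable scan for those lost to follow-up before month 12. The Study Summary limits the primary analysis to participants who complete the 12-month scan and blood collection. Section 9.3.1 names no all-randomised set and gives no rule for patients removed under 6.7.

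**The concern.** The same toxicity or compliance problem can be handled under 6.6, with recurrence still ascertained, or under 5.10 and 6.7, with only safety calls prescribed. Two sites could act differently and both be following the protocol.

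The primary comparison should count recurrences in everyone randomised, on or off the capsule. If removal before recurrence ends ascertainment, events are lost, and Section 5.11 says patients who withdraw from treatment are not replaced. If removal is also more frequent in one arm and related to recurrence risk, the censoring is informative and the hazard ratio is biased. Toxicity can depend on the arm, and in cirrhotic patients it may also depend on liver status. Removal at recurrence is not at issue, because the TTR event has by then occurred.

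**Working it through.** **Reading the sections together**

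| Situation before recurrence | 6.6 | 6.7 | 5.10 |
|---|---|---|---|
| Toxicity or adverse event | Off agent; endpoint data continue if possible | Off treatment and/or study, not specified | Removed from study; 6.3 calls |
| Non-compliance | Off agent; endpoint data continue if possible | Off treatment and/or study, not specified | Removed from study; 6.3 calls |

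Nothing states which section prevails. Section 5.3.2 shows that the protocol treats off treatment and off study as different states, yet 6.7 does not assign its reasons to one or the other.

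**Inputs (Sections 9.2 and 9.3.1)**

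These are 65 randomised per arm, 12-month recurrence of 35% in controls, competing events of 20%, hazard ratio 0.45, two-sided alpha 0.10 and 10% drop-out. TTR is limited to 12 months (Section 2.3).

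**Step 1. Hazards.** With exponential times, the total control hazard is −ln(1 − 0.55)/12 = 0.0665 per month.
- Recurrence: 0.0665 × 35/55 = 0.0423.
- Competing events: 0.0665 × 20/55 = 0.0242.
- A hazard ratio of 0.45 gives 0.0191 for recurrence on pravastatin and a 12-month incidence of (0.0191/0.0433) × (1 − e^(−12 × 0.0433)) = 17.8%, matching the plan's 18%.

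**Step 2. The plan's power.** With 47 per group, 42 months of accrual, 15 months of follow-up and 10% drop-out per 12 months, these hazards give 37.8 events. Schoenfeld power is Φ(½ × √37.8 × |ln 0.45| − 1.645) = 79%, so the stated 80% reproduces. The lower figures below arise because TTR stops at 12 months, which is a separate matter.

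**Step 3. Lost events, 65 per arm, 12-month window.**
- Full follow-up: 65 × (0.350 + 0.178) = 34.3 events. Power is Φ(½ × √34.3 × 0.7985 − 1.645) = 75.6%.
- All 10% drop-out treated as removal with censoring: the added hazard is −ln(0.9)/12 = 0.0088, the incidences fall to 33.5% and 17.0%, and events are 32.8. Power is 73.9%.
- With 5% or 20% removed (assumed range): 33.6 or 31.2 events, power 74.8% or 72.1%.

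**Step 4. Bias when the true hazard ratio is 1.** The documents give no removal rates by arm, so all of these are assumed. Removal occurs in the first 6 months and is confined to a fifth of patients with a higher recurrence hazard. The simulation used 1.5 million per arm (Monte Carlo error about 0.002).

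| Removed, pravastatin vs placebo | Hazard 1.5 times | Hazard 2 times |
|---|---|---|
| 10% vs 5% | 0.99 | 0.98 |
| 20% vs 5% | 0.96 | 0.93 |
| 6% vs 4% | 0.99 | 0.99 |

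With equal hazards the estimate is 1.00 throughout. For scale, about 65 × 0.70 = 45.5 events are expected under the null, so the standard error of the log hazard ratio is about 2/√45.5 = 0.30. The largest bias, |ln 0.93| = 0.07, is about a quarter of that.

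A second simulation used 65 per arm, with removal confined to a half at three times the hazard. It gave 0.94 to 0.99 and rejection rates of 9.4% to 11.1% against the nominal 10%.

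**The case against.** The strongest reply is that the protection already exists. Section 6.6 continues endpoint collection, and Section 5.4 handles the named drug toxicities by stopping the agent, not participation. Section 3.1.3 sends all standard-of-care scans for central review. Section 6.7 is permissive, and only withdrawal of consent expressly ends follow-up. The triggers also differ: 6.6 lists any adverse event, whereas 6.7 requires that continuing in the protocol be unsafe. This stands as a limit on the point, but it does not settle it. Section 5.10 is mandatory in wording, covers every 6.7 reason and cites only the calls, and 6.6 is qualified by feasibility.

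A reader might infer more than the documents support.

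- **That scans stop at removal.** No section says so; 5.10 merely does not provide for them.
- **That Section 2.3 censors these patients.** Its rule names only loss to follow-up. Applying it to removals is an extension, natural but unstated.
- **That TTR becomes an on-treatment comparison.** Section 9.3.1 does not censor at drug stop, and other off-agent reasons, such as supply or concomitant medication, keep follow-up under 6.6.
- **That the bias is large.** The 0.93 end needs every higher-risk pravastatin patient to be marked for removal. The plan's own safety figures do not suggest a large excess: myalgia about 5% and rhabdomyolysis or raised creatine kinase under 1% (Section 1.2), persistent transaminase rises about 1% (Section 7.1), and ALT doubling 8% on pravastatin against 13% on placebo in the cited trial (Section 1.2).
- **That all drop-out is recoverable.** The 10% also covers withdrawn consent and true loss, which no wording can recover.

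**Conclusion.** The conflict between 5.10, 6.6 and 6.7 is in the text and should be resolved, because following 5.10 as written may lose TTR events in patients who have not recurred. The Study Summary's completer restriction adds to the problem, since removed patients could be excluded altogether.

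The size is modest. Power falls from about 76% to no lower than 74% if removal acts as censoring and accounts for all of the planned drop-out. The null hazard ratio is shifted to between 0.93 and 0.99 under the assumed unequal, risk-related removal. There is no bias if removal is unrelated to recurrence risk, and the direction reverses if lower-risk patients are the ones removed. The type I error rate stays close to nominal in the scenarios run. The case for acting rests on a real contradiction with a nearly free remedy, not on a large expected bias.

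**What to change.** Reconcile Sections 5.10, 6.6, 6.7 and 2.3 and the Study Summary.

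1. State in 6.7 and 5.10 that stopping the agent or study procedures does not end endpoint collection, except on withdrawal of consent to follow-up, death or true loss to follow-up. Define true loss once: Section 4.5 uses two months of failed rescheduling and 6.7 uses two years.
2. Point 5.10 to 6.6 as well as 6.3.
3. Continue to collect standard-of-care scans from the record and send them for central review through month 12.
4. State in 2.3 how TTR is censored for patients removed under 6.7.
5. Analyse TTR in all randomised participants as randomised, in place of the 12-month-completer set.

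No change is proposed to when the drug is stopped or to a physician's ability to withdraw a patient from study procedures. The cost is wording, a little more record review and the transfer of scans already done as standard care. No visits or procedures are added.
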